2.3 Exploratory Objectives and Other Assessments

- TTP, RR, PFS, OS, TTF, AFP response, and toxicity and tolerability will be described in subsets defined by HBV, HCV, Asian, and non-Asian status.
- To enumerate CTC at baseline and after 1 and 2 cycles of therapy to evaluate for any relationship between baseline levels and change in levels with median TTP and/or OS
- To characterize baseline mTOR pathway activation by immunohistochemistry (IHC) for selected markers such as pS6RP, pAKT, PTEN, and LKB1, and by tumor next-generation DNA sequencing of targeted genes including mTOR pathway in archival tumor specimens from HCC patients treated with temsirolimus plus sorafenib.
- To examine the relationship between baseline mTOR pathway activation by IHC and by sequencing and clinical outcomes on treatment with temsirolimus plus sorafenib.
- In patients with chronic active HBV infection or exposure, to monitor hepatitis viral load during and after therapy with an mTOR inhibitor
- To bank peripheral blood specimens and left-over archival pathology or cytology specimens for future research

2.4 Endpoints

2.4.1 Primary Endpoint

- Median TTP will be calculated in months from date of first dose of protocol therapy to date of removal from study for progression. For patients removed from study for other reasons than progression (such as toxicity, withdrawal of consent, death without documented progression, or other reasons without clinical or radiographic evidence of tumor progression), TTP will be censored at the date last known to be progression-free.

2.4.2 Secondary Endpoints

- Response rate (RR) will be measured by RECIST version 1.1.
- Median PFS will be calculated in months from date of first dose of protocol therapy to date of documented disease progression or death from any cause. For patients removed from study for other reasons than progression or death, PFS will be censored at the date last known to be progression-free.
- Median OS for all enrolled patients who receive at least one dose of protocol therapy will be calculated from date of first dose of protocol therapy until date of death, using chart review and/or follow up phone calls to determine date of death in patients after removal from study.
- TTF will be measured from date of first dose of protocol therapy to date of study discontinuation for progression, death, or adverse events (related or unrelated). For patients removed from study for other reasons (such as noncompliance or withdrawal of consent), TTF will be censored at the date of study discontinuation.
- In patients with baseline AFP ≥ 20 ng/mL, AFP response will be measured by the percent change from baseline value to the value at the time of best AFP response. The proportion

of $\geq 50\%$ decline from baseline will be measured. The change in AFP will also be examined for association with absolute TTP and best response.

- Toxicity will be measured using Common Terminology Criteria for Adverse Events (CTCAE) version 4.0. The frequency of dose reduction, treatment delays, and discontinuation for lack of tolerability will be quantified.

2.4.3 Exploratory Endpoints

- TTP, RR, PFS, OS, TTF, AFP response, and toxicity and tolerability will be described in subsets defined by HBV, HCV, Asian, and non-Asian status.
- CTC will be enumerated in peripheral blood at baseline and after 1 and 2 cycles of therapy to evaluate for any relationship between baseline levels and change in levels with median TTP and/or OS.
- Baseline mTOR pathway activation status as measured by immunohistochemistry (IHC) for selected markers such as pS6RP, pAKT, PTEN, and LKB1, and by a targeted next-generation tumor DNA sequencing panel including mTOR pathway genes in archival tumor specimens.
- Relationship between baseline mTOR pathway activation by IHC and/or sequencing and clinical outcomes including TTP and AFP response.
- In patients with chronic active HBV and/or positive HBcAb, hepatitis B viral DNA quantitative will be monitored for rates of viremia/reactivation on study.
- Optional patient blood specimens (including serum, PBMC, whole blood, and plasma) and left-over archival pathology or cytology specimens will be banked in the UCSF Hepatobiliary Tissue Bank for future research.

3. Study Design

3.1 Characteristics

This study is a single-arm, one-stage, open-label phase II trial to evaluate the efficacy of the combination of temsirolimus plus sorafenib in first line therapy for patients with histologically-confirmed advanced HCC.

3.2 Number of Subjects

The target sample size is 25 evaluable patients for the primary endpoint. With the expectation of approximately 10% ineligibility rate, the expected maximum enrollment will be 28 patients. Eligible patients who receive at least one dose of protocol therapy will not be replaced. Patients will be replaced and removed from study if determined to be ineligible after enrollment (for reasons such as inability to comply/withdrawal of consent or other ineligibility)

3.3 Eligibility Criteria

The study population will be patients with advanced, unresectable HCC with adequate performance status and Child-Pugh class A or B with ≤ 7 points liver function who have not received prior systemic therapy including no prior sorafenib.

Patients must have baseline evaluations performed prior to the first dose of study drug and must meet all inclusion and exclusion criteria. In addition, the patient must be thoroughly informed about all aspects of the study, including the study visit schedule and required evaluations and all regulatory requirements for informed consent. The written informed consent must be obtained from the patient prior to enrollment. The following criteria apply to all patients enrolled onto the study unless otherwise specified.

3.3.1 Inclusion Criteria

1. Patients must have histologically diagnosed AJCC stage II, III, or IV HCC not eligible for curative resection, transplantation, or ablative therapies
 - a. Cases with mixed, composite, or combined HCC-cholangiocarcinoma histology are eligible with approval from study chair and provided the treating investigator believes it is in the best interest of the patient to treat the tumor with therapy targeted towards the HCC component of tumor based upon review of pathology and clinical characteristics
2. Radiographically measurable disease by RECIST version 1.1 in at least one site not previously treated with chemoembolization, radioembolization, or other local ablative procedures (i.e. must have at least one measurable target lesion, either within the liver or in a measurable metastatic site); a new area of tumor progression within or adjacent to a previously-treated lesion, if clearly measurable by a Radiologist, is acceptable
3. No prior systemic cytotoxic chemotherapy or targeted therapy (including sorafenib) for HCC
4. Prior chemoembolization, local ablative therapies, or hepatic resection permitted if completed ≥ 4 weeks prior to study enrollment if patient has recovered with \leq grade 1 toxicity and if measurable disease (criterion 2) is present
5. Prior radiation for bone or brain metastases is permitted if patient is now asymptomatic and has completed all radiation and steroid therapy (if applicable) for brain or bone metastases ≥ 2 weeks prior to study enrollment.
6. Age ≥ 18 years.
7. Child-Pugh score of A or B with ≤ 7 points and meeting laboratory eligibility for all parameters
8. ECOG performance status of 0 or 1
9. Life expectancy greater than 3 months
10. Treatment with appropriate antiviral therapy for patients with active HBV infection is required
11. Treatment for clinically-significant hyperglycemia, hyperlipidemia, or hypertension that develops on study is required
12. Baseline blood pressure must be adequately controlled with or without antihypertensive medications prior to enrollment (systolic ≤ 150 mm Hg, diastolic ≤ 90 mm Hg)
13. Baseline cholesterol must be < 350 mg/dL and triglycerides < 300 mg/dL (with or without the use of antihyperlipidemic medications)
14. Baseline fasting blood glucose must be ≤ 140 mg/dL and hemoglobin A1c less than 7.5% (with or without the use of anti-diabetic medications)
15. Adequate baseline organ and marrow function as defined below

Adequate bone marrow function:

absolute neutrophil count $\geq 1,000/\text{mcl}$
platelets $\geq 75,000/\text{mcl}$

hemoglobin ≥ 8.5 g/dL

Adequate hepatic function:

total bilirubin ≤ 2 mg/dL or ≤ 1.5 times ULN

AST(SGOT) & ALT (SGPT) ≤ 5 X ULN

INR ≤ 1.5 X ULN

Adequate renal function:

albumin ≥ 2.8 g/dL

creatinine ≤ 1.5 X ULN

16. Able to tolerate oral therapy.
17. Ability to understand and willingness to provide informed consent, and the willingness to comply with the requirements of the protocol. Informed consent may be obtained with the assistance of a medical translator according to institutional policies.
18. The effects of temsirolimus on the developing human fetus are unknown. For this reason and because sorafenib - also being used in this trial - is known to be teratogenic, women of child-bearing potential must have a negative pregnancy test within 14 days of study enrollment.

Also, women of child-bearing potential and men must agree to use two methods adequate contraception (hormonal plus barrier or two forms of barrier) or abstinence prior to study entry and for the duration of study participation. Should a woman become pregnant or suspect she is pregnant while she or her partner is participating in this study, she needs to inform her treating physician immediately. Men treated or enrolled on this protocol must also agree to use adequate contraception prior to the study, or be surgically sterile, for the duration of study participation, and for 3 months after completion of study drug administration.

19. Eligibility of patients receiving any medications or substances known to affect or with potential to affect the activity or pharmacokinetics of temsirolimus and/or sorafenib will be determined following review of the case by the Study Chair. Efforts should be made to switch patients who are taking enzyme-inducing anti-convulsant agents to other medications. A list of medications and substances known or with the potential to interact with selected relevant CYP450 isoenzymes, P-glycoprotein pathway, and/or UGT1A1 glucuronidation is provided in *Appendices 6-9*.

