Clearance of the mTOR inhibitor everolimus in patients with hepatic dysfunction is markedly reduced, leading to the recommendation that everolimus dosage should be reduced in the setting of impaired hepatic function.(Dancey 2006) A pharmacokinetic and pharmacodynamic study of temsirolimus in patients with advanced malignancies and varying degrees of liver dysfunction showed no significant difference in temsirolimus exposure in patients with mild to moderate liver dysfunction; in patients with Child-Pugh score of C, however, exposure to temsirolimus and its metabolite was increased.(Pfizer 2011) This study was conducted by the National Cancer Institute (NCI) Organ Dysfunction Working Group (ODWG) and was presented at the American Society of Clinical Oncology Annual Meeting in 2011.(Sarantopoulos 2011) The authors demonstrated decreased clearance, prolonged half-life, and increased AUC in patients with greater degrees of hepatic dysfunction. According to Prescribing Information, a reduction in temsirolimus starting dose to 15 mg weekly is recommended in patients with mild to moderate liver dysfunction as defined by bilirubin > 1 to 1.5 times ULN and/or AST > ULN but bilirubin within normal limits, and temsirolimus is contraindicated in patients with total bilirubin greater than 1.5 times the upper limit of normal.(Wyeth 2011)

Strong inducers of CYP3A4/5 may decrease exposure to temsirolimus and sirolimus and should be avoided. Strong inhibitors of CYP3A4 may increase exposures and should be avoided.

Moderate CYP3A4 inhibitors should be used with caution or substituted with an alternate agent. Other agents and classes with potential for drug interactions with temsirolimus are reviewed in *Section 6.7 and Appendices 6-9 Prohibited Medications*.

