Elimination is primarily via the feces. After a single IV dose of [14C]-temsirolimus approximately 82% of total radioactivity was eliminated within 14 days, with 4.6% and 78% of the administered radioactivity recovered in the urine and feces, respectively. Following a single 25 mg dose of TORISEL® in patients with cancer, temsirolimus mean (CV) systemic clearance was 16.2 (22%) L/h. Temsirolimus exhibits a bi-exponential decline in whole blood concentrations and the mean half-lives of temsirolimus and sirolimus were 17.3 hr and 54.6 hr.

Temsirolimus is a substrate of the efflux transporter P-glycoprotein (Pgp) *in vitro*. If TORISEL® is administered with drugs that inhibit Pgp, increased concentrations of temsirolimus are likely, and caution should be exercised. *In vitro*, temsirolimus inhibited human Pgp (IC50 value of 2µM). If TORISEL® is administered with drugs that are substrates of Pgp, increased concentrations of the substrate drug are likely and caution should be exercised.

No dosage adjustment for temsirolimus is recommended in patients with renal impairment. There have been no clinical studies of this agent in patients with impaired renal function, though renal impairment is not expected to markedly influence drug exposure. Less than 5% of total radioactivity was excreted in the urine following a 25 mg intravenous dose of [14C]-labeled

temsirolimus in healthy subjects. Temsirolimus has not been studied in patients undergoing hemodialysis.

Temsirolimus is cleared predominantly by the liver.

Contraindications

Temsirolimus IV is contraindicated in persons with known hypersensitivity to temsirolimus or any component of the formulation. Temsirolimus is contraindicated in patients with bilirubin >1.5 x ULN.

Availability

Temsirolimus is FDA-approved for the treatment of advanced renal cell carcinoma (RCC). Temsirolimus will be supplied for this trial directly by the manufacturer, Pfizer, Inc., from commercial supplies. See *Section 4.2 Drug Accountability*.

Storage and handling

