	Grade 3	Hold both drugs until ≤ Grade 2, then decrease TEM by 1 DL and continue SOR at same dose; if recurs, hold both drugs until ≤ Grade 2, then decrease SOR by 1 DL and continue TEM at same dose; continue alternating dose reductions if toxicity recurs	
	Grade 4	Hold both drugs until ≤ Grade 2, then decrease both drugs by 1 DL	
Diarrhea (despite optimal supportive care)	Grade 1	No change	No change
	Grade 2	No change	No change
	Grade 3	Hold both drugs until ≤ Grade 2, then decrease SOR by 1 DL and continue TEM at same dose; if recurs, hold both drugs until ≤ Grade 2, then decrease TEM by 1 DL and continue SOR at same dose; continue alternating dose reductions if toxicity recurs	
	Grade 4	Hold both drugs until ≤ Grade 2, then decrease both drugs by 1 DL	

Toxicity	Grade (NCI CTCAE v4.0)	Temsirolimus Adjustment	Sorafenib Adjustment
HEPATIC DYSFUNCTION			
Hyperbilirubinemia (substitute direct bilirubin values and normal ranges for patients with Gilbert's Syndrome)	Grade 1 (BILT > ULN to 1.5 times ULN)	No change	No change
	Grade 2 (BILT > 1.5 to 3 times ULN)	Hold both drugs and recheck weekly until ≤ Grade 1, then decrease SOR by 1 DL and continue TEM at same dose; if recurs, hold both drugs and recheck weekly until ≤ Grade 2, then decrease TEM by 1 DL and continue SOR at same dose; continue alternating dose reductions if toxicity recurs	
	Grade 3 (BILT > 3 to 10 times ULN)	Hold both drugs and recheck weekly until ≤ Grade 1, then decrease both drugs by 1 DL	
	Grade 4 (BILT > 10 times ULN)	Discontinue protocol therapy	
Transaminase and alkaline phosphatase elevation (if assessed as treatment-related, clinically relevant, and ≥ 2 grades from baseline)	Grade 1 (> ULN to 2.5 times ULN)	No change	No change
	Grade 2 (> 2.5 to 5 times ULN)	No change	No change
	Grade 3 (> 5 to 20 times ULN)	Hold both drugs and recheck weekly until ≤ Grade 2, then decrease SOR by 1 DL and continue TEM at same dose; if recurs, hold both drugs and recheck weekly until ≤ Grade 2, then decrease TEM by 1 DL and continue SOR at same dose; continue alternating dose reductions if toxicity recurs	
	Grade 4 (> 20 times ULN)	Discontinue protocol therapy	
Ascites	Grade 1 (Asymptomatic)	No change	No change

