5.3 Management of Toxicities

Each patient receiving at least 1 dose of temsirolimus in combination with at least 1 dose of sorafenib will be evaluable for safety. The safety parameters include all laboratory tests and hematological abnormalities, physical findings, and spontaneous reports of adverse events reported to the investigator by patients.

Each patient will be assessed periodically for the development of any toxicity as outlined in Table 6.1, Schedule of Study Procedures and Assessments. Toxicity will be assessed according to the NCI [CTCAE v4.0](#). Dose adjustments, treatment delay, and treatment discontinuation will be determined according to the system showing the greatest degree of toxicity. Toxicity will be formally assessed at protocol-defined assessment timepoints well as by investigator review of weekly laboratory testing and, in the interim, by patient contact with the study coordinator and/or treating investigator should new symptoms arise between visits. General principles of toxicity management are listed below:

- Temsirolimus and sorafenib will be dose-adjusted according to investigator's attribution of toxicity. In equivocal cases, the decision may be made by treating investigator.
- Asymptomatic changes in laboratory values require dose modification only if assessed to be treatment-related, clinically relevant, and represent a change of ≥ 2 grades from baseline.
- If toxicity occurs, supportive care medications should be applied to ameliorate signs and symptoms (including antiemetics for nausea and vomiting, antidiarrheals for diarrhea, antipyretics and antihistamines for drug fever, antihypertensives for hypertension, and phosphate repletion for hypophosphatemia) before toxicity grade is determined.

- A patient will be removed from protocol therapy if either of the two study drugs is discontinued.
- Temsirolimus will be discontinued if it is not tolerated at a dose of 5 mg IV weekly.
- Sorafenib will be discontinued if it is not tolerated at a dose of 200 mg PO every other day.
- Once a dose has been reduced for toxicity, it should not be re-escalated.
- In obese patients, all dosing is to be determined by the patient's actual body weight.
- If there is more than one indication for dose modification, use the more strict dose modification (i.e. modify according to the most severe toxicity).

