9.2.2 Accrual estimates

It is estimated that 12 patients will be accrued annually (approximately 1 patient per month) combined between UCSF and Northwestern. This estimate is based upon the accrual to the predecessor Phase I study of this combination which enrolled 25 patients with similar eligibility criteria between December 2009 and April 2012. It is expected that the Phase II study will accrue faster than the Phase I due to the established infrastructure and momentum from the Phase I study, along with no requirement for delays for dose escalation and frequent amendments which were associated with the Phase I study.

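### The bilirubin entry limit in criterion 15 can admit patients above the 1.5 × ULN level at which the protocol calls temsirolimus contraindicated, wherever the local ULN is below 1.33 mg/dL

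*Combined protocol and SAP*

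**What the plan says.** Criterion 15 in section 3.3.1 sets the hepatic entry limit as "total bilirubin ≤ 2 mg/dL or ≤ 1.5 times ULN". It does not say which limit governs when they differ.

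Two other places state a contraindication. Section 1.2.3, citing the prescribing information, says "temsirolimus is contraindicated in patients with total bilirubin greater than 1.5 times the upper limit of normal". Section 4.1.1, under Contraindications, says "Temsirolimus is contraindicated in patients with bilirubin >1.5 x ULN" and attaches no exception. The label's reduced starting dose of 15 mg, also described in section 1.2.3, is for "mild to moderate liver dysfunction as defined by bilirubin > 1 to 1.5 times ULN" (or for raised AST with normal bilirubin), so it offers nothing above 1.5 × ULN.

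For patients on treatment, the hyperbilirubinemia row of the table in section 5.2.3 defines "Grade 2 (BILT > 1.5 to 3 times ULN" and holds both drugs until the value is back to Grade 1 or lower. For Gilbert's Syndrome that row says to "substitute direct bilirubin values and normal ranges for patients with" the condition. Section 5.3 adds a general rule: "Asymptomatic changes in laboratory values require dose modification only if assessed to be treatment-related, clinically relevant", and only if the change is at least two grades from baseline.

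**The concern.** A patient can satisfy criterion 15 through the 2 mg/dL limit while standing above 1.5 × the local ULN. The protocol would then accept someone for whom, by its own account, one of the two study drugs is contraindicated. This matters more than usual here. The population has liver dysfunction up to Child-Pugh B7, both drugs are cleared mainly by the liver, and section 1.2.2.2 itself raises concern about added toxicity in such patients.

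The same patient would start in the dose table's Grade 2 range. One part of the protocol then says to hold both drugs, and another can be read as requiring no change.

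**Working it through.** The plan gives no figure to reproduce, so the check is threshold arithmetic followed by a search for anything that closes the gap.

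**Inputs.** Entry limits of 2 mg/dL and 1.5 × ULN (section 3.3.1, criterion 15). Contraindication above 1.5 × ULN (sections 1.2.3 and 4.1.1). The ULN is not given; section 10.11 has the participating site supply its own laboratory normals. I therefore assume a range of 1.0 to 1.5 mg/dL.

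**Highest eligible value.** Under *or*, the ceiling is max(2, 1.5 × ULN). It exceeds 1.5 × ULN only when 2 > 1.5 × ULN, that is, when ULN < 2 / 1.5 = 1.33 mg/dL.

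| Assumed ULN (mg/dL) | 1.5 × ULN | Highest eligible | As multiple of ULN | Width of conflict (mg/dL) |
|---|---|---|---|---|
| 1.0 | 1.50 | 2.00 | 2.00 | 0.50 |
| 1.1 | 1.65 | 2.00 | 1.82 | 0.35 |
| 1.2 | 1.80 | 2.00 | 1.67 | 0.20 |
| 1.3 | 1.95 | 2.00 | 1.54 | 0.05 |
| 1.4 | 2.10 | 2.10 | 1.50 | 0 |
| 1.5 | 2.25 | 2.25 | 1.50 | 0 |

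Example: 1.9 mg/dL at an assumed ULN of 1.2 is 1.9 / 1.2 = 1.58 × ULN. The patient is eligible by the first limit and contraindicated by section 4.1.1.

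**Does another criterion close the gap?**

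- Section 3.3.2 contains no bilirubin limit.
- Criterion 7 requires Child-Pugh ≤ 7 points and otherwise points back to the laboratory limits. Under Appendix 2, with the other four items in their best category (1 point each), bilirubin below 2 mg/dL gives 1 + 4 = 5 and bilirubin of 2 to 3 mg/dL gives 2 + 4 = 6. Both are class A.
- Of the two contraindications in section 4.1.1, hypersensitivity is carried into exclusion criterion 18. The bilirubin limit is not carried over intact.

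**Would such a patient be dosed?** The hyperbilirubinemia row has no change-from-baseline qualifier, whereas the transaminase and creatinine rows do. Read alone, it holds both drugs across the whole conflict range. The section 5.3 rule covers asymptomatic laboratory changes in general, and a stable baseline value is a change of zero grades, so it can be read as requiring no hold. The text does not say which reading governs.

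**The case against.** The best defence is that the wider limit was chosen for a liver-cancer population. The contraindication restates the label of a drug approved for renal cell carcinoma, where the phase III dose was 25 mg. This trial gives 10 mg, below even the label's reduced 15 mg. The 2 mg/dL figure coincides with a Child-Pugh bilirubin boundary. The preceding phase I study, "which enrolled 25 patients with similar eligibility criteria", arrived at the 10 mg dose. Section 1.2.3 reports no significant exposure difference in mild to moderate dysfunction.

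These facts make the limit plausible, but the protocol never uses them to set the contraindication aside. The phase I remark is part of an accrual estimate. The exposure evidence is mixed. Section 1.2.3 also reports slower clearance and higher AUC with greater dysfunction. Section 1.2.3.2 reports that single-agent AUC at 10 mg in the phase I cohort looked similar to that of non-HCC subjects at 25 mg, although it fell significantly once sorafenib was added.

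Two parts of the defence do stand. First, the effect may be small or absent: only two sites are named, their ULNs are unknown, and at an assumed 1.3 mg/dL with results reported to 0.1 the conflict is the single value 2.0. Second, a reader might infer that the plan will dose patients against a contraindication. The documents do not support that. Bilirubin is checked again on Cycle 1 Day 1 and weekly after that, the dose table can be read as holding both drugs, and the investigator may delay or stop treatment for safety. These safeguards limit harm after entry; they do not set the entry limit.

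**Conclusion.** The inconsistency holds as a matter of wording. Criterion 15 and the stated contraindication disagree at any ULN below 1.33 mg/dL, by 0.50 down to 0.05 mg/dL for assumed ULNs of 1.0 to 1.3, and nothing else in the protocol reconciles them. That part is certain. Whether either site has a ULN in that range, how many patients would fall in the band, and whether they would be dosed cannot be settled from the documents.

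It would also be wrong to infer any effect on the efficacy result: no endpoint, sample size or analysis depends on this limit. It is an eligibility and safety inconsistency that should be corrected.

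**What to change.** Change criterion 15 to total bilirubin ≤ 1.5 × ULN, or keep both figures and require the lower of 2 mg/dL and 1.5 × ULN. Either wording brings the gap to zero at every ULN. The first still allows values above 2 mg/dL where the ULN exceeds 1.33; the second does not. With either, nobody meets the criterion with a value in the Grade 2 range, so the unclear hold rule no longer matters at that point.

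Do not carry the dose table's direct-bilirubin substitution for Gilbert's Syndrome into the entry criterion. Section 1.2.3 states the contraindication for total bilirubin, and an uncapped exception would widen entry. At an assumed ULN of 1.2, a total of 2.5 mg/dL is 2.5 / 1.2 = 2.08 × ULN. That patient is ineligible today, since 2.5 exceeds both 2 and 1.8 mg/dL, but could qualify on direct bilirubin under such an exception.

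The cost is a one-line amendment and the loss of a few borderline patients from a trial expecting about 12 a year. Sample size and analysis stay as they are.
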